4.4.3. Bioanalytical and Pharmacokinetic/Pharmacodynamic Methods

PK/PD analyses to address secondary and exploratory objectives of this study will be described by Lilly in separate PK/PD analysis plans. Conduct of the PK/PD analyses will be the responsibility of Eli Lilly and Company.

The PK/PD analyses will be initiated up to approximately three weeks before the planned database lock dates. All analyses will be performed by unblinded Lilly PK personnel, who are unblinded to subject treatment assignments to support dose adjustments. Results from the PK/PD analyses will not be shared with site or blinded study team personnel prior to the respective database lock.

4.5. Tertiary/Exploratory Endpoints Analyses

4.6. Safety Analyses

All safety data will be descriptively summarized by treatment groups and analyzed based on the safety population as defined in Section 3. The safety analyses include AEs, safety in special groups and circumstances, including Adverse Events of Special Interest (AESI), laboratory analytes, QIDS-SR16, C-SSRS, ECGs, and vital signs. The duration of exposure will also be summarized. The categorical safety measures will be summarized using incidence rates and analyzed by Fisher's exact test. The mean change in the continuous safety measures including vital signs, QIDS-SR16, physical characteristics, and laboratory values will be summarized by visits and analyzed by ANCOVA, with treatment and baseline values in the model. More details are provided in subsequent sections.

For specific events of special interest (see Section 4.6.3 for more details), an incidence rate, IR per 100 patient-years of observation (PYO), will be provided. Patient-years of observation will be calculated as the sum of all patient observation time in the treatment group. For a patient with an event, the observation time will be censored at the event date; for a patient without the event, the observation time will be counted until the patient's last treatment dose date plus 30 days or the patient's last visit, whichever occurs first. Only events that occur within 30 days after the patient's treatment discontinuation date will be considered.

See formula as follows:

$$\begin{aligned}
 PYO = & \sum_{pt \ w \ event} \frac{event \ start \ date - first \ trt \ dose \ date + 1}{365.25} \\
 & + \sum_{pt \ w/o \ event} \frac{last \ observation \ date - first \ trt \ dose \ date + 1}{365.25}
 \end{aligned}$$

Incidence rate will be calculated as follows:

$$IR = \frac{\text{unique number of patients with event}}{PYO} \times 100$$

For each IR provided, a 95% CI will be calculated based on the Poisson distribution. Treatment group comparisons based on IR will be provided based on the incidence rate difference (IRD) together with its 95% CI.

Not all displays described in this section will necessarily be included in the CSRs. Any display described and not provided in the CSR would be available upon request. Not all displays will necessarily be created as a “static” display. Some may be incorporated into interactive display tools instead of or in addition to a static display. Any display created interactively will be included in the CSR if deemed relevant to the discussion.

4.6.1. Extent of Exposure

Duration of exposure to study treatment (defined as time since first injection of study treatment in days) will be summarized by treatment group during the Induction Period, the Maintenance Period, and the Extension Period.

Duration of exposure during the Induction Period for the Safety Population will be calculated as:

(Disposition date (for those who have discontinued the Induction Period), OR Maintenance/Extension Start date -1 (for those who have completed the Induction Period), OR Date of last study visit in the Induction Period (for those who are still being treated in the Induction Period) – Date of first injection of study treatment + 1)

Duration of exposure during the Maintenance Period will be calculated as:

(Disposition date (for those who have discontinued the Maintenance Period), OR Date of last study visit in the Maintenance Period (for those who are still being treated in the Maintenance Period) – Date of the Visit 10 injection of study treatment + 1)

Duration of exposure to LY3471851 during the Extension Period will be calculated as:

(Disposition date (for those who have discontinued the Extension Period), OR Date of last study visit in the Extension Period (for those who are still being treated in the Extension Period) – Date of the Visit 10 injection of study treatment + 1)

Duration of exposure to LY3471851 for the combined Induction Period and Maintenance Period will be calculated as:

(Disposition date (for those who have discontinued the Maintenance Period), OR Date of last study visit in the Maintenance Period (for those who are still being treated in the Maintenance Period)– Date of first injection of LY3471851 + 1)

Duration of exposure to LY3471851 for the combined Induction Period and Extension Period will be calculated as:

(Disposition date (for those who have discontinued the Extension Period), OR Date of last study visit in the Extension Period (for those who are still being treated in the Extension Period)– Date of first injection of LY3471851 + 1)

The date of first injection of LY3471851 is defined in [Table KFAH.4](#)**Error! Reference source not found.**

Table KFAH.4. First Injection of LY3471851 by Treatment Group

	Visit of first LY3471851
All patients randomized to LY3471851 (regardless of Week 12 response status)	Week 0 (Visit 2)
Week 12 Inadequate Responders originally randomized to placebo and assigned to LY3471851 at Visit 10	Week 14 (Visit 10)

Descriptive statistics (n, mean, SD, minimum, first quartile, median, third quartile, and maximum) will be provided for patient-days of exposure and the frequency of patients falling into different exposure ranges will be summarized. Exposure ranges are as follows:

- >0, ≥ 4 weeks, ≥ 12 weeks, and ≥ 52 weeks.
- >0 to <4 weeks, ≥ 4 weeks to <12 weeks, ≥ 12 weeks to <52 weeks, and ≥ 52 weeks.

Additional exposure ranges may be considered if necessary.

A by-patient listing of exposure duration will be provided.

Patients who had dose modification will be grouped under the randomized treatment arm and will not be grouped by the modified dose amount.

No inferential analysis for comparison between treatment arms will be performed.

4.6.2. Adverse Events

4.6.2.1. Adverse Events

Adverse events are recorded in the eCRF. Each AE will be coded to SOC and PT, using the *Medical Dictionary for Regulatory Activities* (MedDRA) version that is current at the time of database lock. Severity of AEs is recorded as mild, moderate, or severe.

Treatment-emergent adverse events (TEAEs) are defined as events that either first occurred or worsened in severity after the first dose of study drug and the earliest of the visit study drug disposition date or the last visit date during the treatment period, whichever occurred first, and up to 30 days after study treatment discontinuation. The MedDRA Lowest Level Term (LLT) will be used in defining which events are treatment-emergent. The maximum severity for each LLT during the baseline period until the first dose of the study medication will be used as baseline. If an event is preexisting during the baseline period, but it has missing severity, and the event persists during the treatment period or up to 30 days after treatment discontinuation, then the baseline severity will be considered mild for determining any postbaseline treatment-emergence (i.e., the event is treatment-emergent unless the severity is coded mild at postbaseline). If an event occurring postbaseline has a missing severity rating, then the event is considered treatment-emergent. Should there be insufficient data for an AE start date to make this comparison (e.g., the AE start year is the same as the treatment start year, but the AE start month and day are missing), the AE will be considered treatment-emergent. For events occurring on the day of the first dose of study treatment, the day of the onset of the event will

both be used to distinguish between pretreatment and posttreatment in order to derive treatment-emergence.

In general, summaries will include the number of patients in the safety population (N), frequency of patients experiencing the event (n), and relative frequency (i.e., percentage; $n/N*100$).

In an AE overview table, the number and percentage of patients in the safety analysis set who experienced death, a serious adverse event (SAE), any TEAE, permanent discontinuation from study drug due to an AE, or a severe TEAE will be summarized by treatment group.

The number and percentage of patients with TEAEs will be summarized by treatment group in 2 formats listed below. For events that are gender specific, the denominator and computation of the percentage will only include patients from the given gender.

- by MedDRA PT nested within SOC with SOCs ordered alphabetically, and events ordered within each SOC by decreasing frequency in the LY3471851 1800 μ g treatment group.
- by MedDRA PT with events ordered by decreasing frequency in the LY3471851 1800 μ g treatment group.

Adverse events leading to permanent discontinuation of study drug and AEs leading to temporary interruption of study drug will also be summarized by treatment group using MedDRA PT nested within SOC. Events will be ordered by decreasing frequency within SOC in the LY3471851 1800 μ g treatment group.

A summary of temporary interruptions of study drug will also be provided, showing the number of patients who experienced at least 1 temporary interruption and the number of temporary interruptions per patient with an interruption. Further, the duration of each temporary interruption (in days) and the cumulative duration of dose interruption (in days) using basic descriptive statistics (n, mean, SD, minimum, first quartile, median, third quartile, and maximum) will be displayed.

Common TEAEs are defined as TEAEs that occurred in $\geq 1\%$ (before rounding) of patients in any treatment group including placebo. The number and percentage of patients with common TEAEs will be summarized by treatment using MedDRA PT ordered by decreasing frequency in the LY3471851 1800 μ g treatment group.

The number and percentage of patients with TEAEs will be summarized by maximum severity by treatment using MedDRA PT ordered by decreasing frequency for the common TEAEs. For each patient and TEAE, the maximum severity for the MedDRA level being displayed is the maximum postbaseline severity observed from all associated LLTs mapping to that MedDRA PT.

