4.2. Scientific Rationale for Study Design

Primary endpoint definition

The primary endpoint for this study tests the superiority of treatment with LY3471851 versus placebo for clinical remission at Week 12. The endpoint of the MMS was chosen based on available regulatory guidance from the 2016 FDA “Guidance for industry. Ulcerative colitis: clinical trial endpoints” and the 2018 EMA “Guideline on the development of new medicinal products for the treatment of UC.”^{14,31} Both recommend a composite endpoint for both symptomatic and endoscopic remission. The timing of the primary endpoint was based on the PK/PD results of LY3471851 in the Phase 1 single- and multiple-ascending dose studies.

Duration of treatment periods and post-treatment follow-up

The 52-week total duration of treatment was chosen based on the 2018 EMA guideline¹⁴, which recommends at least 12 months for the assessment of long-term efficacy of maintenance of remission.

The post-treatment follow-up period allows for continued safety monitoring after the last dose. A period of 6 weeks for the post-treatment follow-up is considered sufficient to wash out study drug based on the mean half-life, which has been estimated as between 8 to 13 days in the Phase 1 studies.

The inclusion of an extension period for participants who were not clinical responders after the first 12 weeks of treatment is intended to provide additional time for participants on the highest dose to receive potential benefit and respond, and also for participants receiving the lower doses and placebo the opportunity to receive potential benefit and respond to the highest dose.

Choice of control and number of treatment groups

The double-blind, placebo-controlled design of this study limits potential bias in investigator assessments and enables a clearer interpretation of the effects of active drug compared to placebo (background therapy). Nonbiologic background therapy, such as 5-ASA, corticosteroids, AZA, or 6-MP, is allowed in this study with limitations as described in the dose stabilization criteria and listing of allowed concomitant medications. The selection of placebo as a comparator for this study is warranted because study participants will be permitted to use these medications as background therapy.^{13,14}

The use of multiple active dose levels in this study will allow for an evaluation of safety and efficacy across a broad dose range and so provide information to guide dose selection for future studies.

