9.4.4. Safety Analyses

Safety analyses will include AEs, SAEs, AESIs, C-SSRS, QIDS-SR16, vital signs, ECGs, and laboratory analytes, using the Safety Population data descriptively summarized by treatment group. Categorical safety measures will be summarized with incidence rates. Continuous safety measures will be summarized as mean change by visit. Exposure to study intervention will be calculated for each participant and summarized by treatment group.

Adverse events will be coded according to MedDRA and summarized by system organ class, preferred term, severity, and relationship to the study intervention. A TEAE is defined as an event that first occurred or worsened in severity after baseline, with baseline defined as all pre-existing conditions recorded at Visit 1 and any AEs recorded before the first dose of study intervention (that is, during the interval between Visits 1 and 2, and recorded with the time of onset before the first dose of study intervention). The treatment period will be used as the postbaseline period for the analysis. For events that are gender specific, the denominator and computation of the percentage will include only participants from the given gender.

The number and percentage of participants who experienced TEAEs, TEAEs by maximum severity, deaths, SAEs, TEAEs related to study intervention, discontinuations from the treatment due to an AE, and AESIs will be summarized. Treatment-emergent adverse events (all, by

maximum severity), SAEs including deaths, and AEs that lead to treatment discontinuation will be summarized and analyzed by MedDRA SOC and preferred term.

Treatment-related TEAEs (TEAEs related to study intervention) are defined as events that are indicated by the investigator on the eCRF to be related to treatment.

Adverse events of special interest will be identified by a standardized MedDRA query (SMQ) or a Lilly-defined MedDRA preferred term listing.

Follow-up emergent AEs, SAEs including deaths, and AEs that lead to study discontinuation will be summarized. All AEs, including pre-existing conditions, will be listed by participant, visit, preferred term, treatment group, severity, and relationship to the treatment.

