6.7. Appendix 7: List of Planned Laboratory Analytes with Reference
Range Sources.....64

7. **References.....68**

Version history

This Statistical Analysis Plan (SAP) for study J1P-MC-KFAH (KFAH) is based on the protocol dated 18Nov2020 and approved prior to unblinding.

Table KFAH.1. SAP Version History Summary

SAP Version	Approval Date	Change	Rationale
1		Not Applicable	Original version

1. Introduction

Study J1P-MC-KFAH is an adaptive Phase 2, randomized, double-blind, placebo-controlled trial of LY3471851 (NKTR-358) in patients with moderately to severely active ulcerative colitis.

There are no changes to the analyses described in the protocol.

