4.6.2.2. Serious Adverse Events

An individual listing of all AEs including preexisting conditions will be provided. A separate listing will include AEs that led to permanent discontinuation from the study drug. In addition, a listing of AEs that occur more than 30 days after study treatment discontinuation will be provided.

With the International Conference on Harmonisation (ICH) E2A guideline, a SAE is any AE that results in 1 of the following outcomes:

- death
- initial or prolonged inpatient hospitalization
- a life-threatening experience (that is, immediate risk of dying)
- persistent or significant disability/incapacity
- congenital anomaly/birth defect
- considered significant by the investigator for any other reason

The number and percentage of patients who experienced any ICH-defined SAE will be summarized by treatment group during the treatment and follow-up periods using MedDRA PT nested within SOC. Events will be ordered by decreasing frequency within SOC in the LY3471851 1800µg treatment group. In addition, the SAEs will be summarized by treatment group using MedDRA PT without SOC. An individual listing of all SAEs will be provided.

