- Box plots for observed values: Values at each visit (starting at randomization) and change from baseline to each visit and to last postbaseline measure will be displayed in box plots for patients who have a baseline and at least 1 postbaseline visit. For visits included in the treatment period, patients will be included only if the visit occurs on or before the date of treatment discontinuation/completion. Follow-up visit will be the first visit that occurred during the Follow-up period. Individual measurements outside of reference limits will also be displayed using distinct symbols overlaying the box plot. Original-scale data will be used for the display but for some analytes (e.g., immunoglobulins) a logarithmic scale will be used to aid in viewing the measures of central tendency and dispersion. Unplanned measurements will be excluded. Descriptive summary statistics will be included in a table below the box plot. These box plots will be

used to evaluate trends over time and to assess a potential impact of outliers on central tendency summaries. A p-value for change from baseline to endpoint will be provided using an ANCOVA model with explanatory term for treatment and the baseline value as a covariate. Endpoint will be the last observation where patient is on treatment.

- Treatment-emergent high/low analyses: The number and percentage of patients with treatment-emergent high and low laboratory results at any time will be summarized by treatment group. Planned and unplanned measurements will be included. A treatment-emergent **high** result is defined as a change from a value less than or equal to the high limit at all baseline visits to a value greater than the high limit at any time during the treatment period and up to 60 days after treatment discontinuation. A treatment-emergent **low** result is defined as a change from a value greater than or equal to the low limit at all baseline visits to a value less than the low limit at any time during the treatment period and up to 60 days after treatment discontinuation. The Fisher's exact test will be used for the treatment comparisons.

For laboratory analyte measurements collected qualitatively, a listing of abnormal findings will be created. The listing will include patient ID, treatment group, laboratory collection date, analyte name, and analyte finding.

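### Non-serious adverse events starting more than 30 days after treatment stops are listed but not summarised by arm, although the protocol plans a summary of follow-up-emergent events and the SAP declares no change

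*SAP*

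**What the plan says.** **Protocol.** Section 9.4.4 opens by saying that safety data are summarised descriptively by treatment group. It uses the treatment period as the postbaseline period for treatment-emergent adverse events (TEAEs) and then plans a separate follow-up output: "Follow-up emergent AEs, SAEs including deaths, and AEs that lead to study discontinuation will be summarized". Section 8.3.1 collects all AEs to the last post-treatment follow-up visit. Section 4.1 places Visit 801 about 8 weeks after the last dose. Section 4.2 gives the reason for that length: "A period of 6 weeks for the post-treatment follow-up is considered sufficient to wash out study drug based on the mean half-life", with a mean half-life of 8 to 13 days.

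**SAP, AE tables.** Section 4.6.2.1 takes the treatment-emergent window to the earlier of the study drug disposition date and the last treatment-period visit, "whichever occurred first, and up to 30 days after study treatment discontinuation". TEAEs are tabulated by arm. For anything later, Section 4.6.2.2 says "a listing of AEs that occur more than 30 days after study treatment discontinuation will be provided". Serious events (SAEs) are treated differently: they "will be summarized by treatment group during the treatment and follow-up periods using MedDRA PT nested within SOC". No summary of follow-up-emergent AEs is named. The registry table in Section 6.5 limits non-serious events to TEAEs.

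**SAP, incidence rates.** Section 4.6 says "Only events that occur within 30 days after the patient's treatment discontinuation date will be considered". For participants without an event, person-time ends at the last dose plus 30 days or the last visit, whichever comes first. Section 4.6.3.1 applies these rates to serious infections, potential opportunistic infections, herpes zoster and herpes simplex.

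**SAP, changes.** Section 1 states: "There are no changes to the analyses described in the protocol". Section 4.9, whose title promises changes to planned analyses, deals only with protocol deviations.

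**The concern.** The protocol pays for a follow-up visit about 8 weeks after the last dose in order to watch safety while the drug washes out, and it plans to summarise what is seen there. Under the SAP, a non-serious event late in that span, such as a herpes zoster episode, is collected and then appears only in a listing. A reader of the study report could not compare arms on such events without building the table from the listing.

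The change is also undeclared. Protocol 9.4.1 requires changes to the planned analyses that are not principal features to be described and justified in the SAP and the clinical study report.

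The 30-day limit on incidence rates reaches serious events as well. Two SAP outputs on the same kind of event would follow different windows and could disagree with no explanation on the page.

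**Working it through.** **1. Reproduce the protocol's follow-up figure.** The last dose is at Week 50 and V801 is at Week 58. (58 − 50) × 7 = 56 days, which matches the stated 8 weeks. In study days, the last dose is Day 351, Week 52 is Day 365 and V801 is 58 × 7 + 1 = Day 407.

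**2. Part of the washout with no by-arm summary of non-serious AEs.** The SAP does not say whether study treatment discontinuation means the last dose or the disposition date, so both are shown for a completer.

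| Start of the 30 days | Window ends | Uncovered days to V801 | Share of 56 days | Range with V801 ±7 days |
|---|---|---|---|---|
| Last dose (Day 351) | Day 381 | 407 − 381 = 26 | 46% | 19 to 33 |
| Week 52 disposition (Day 365) | Day 395 | 407 − 395 = 12 | 21% | 5 to 19 |

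The TEAE definition mentions the disposition date, which favours 12 days for the AE tables. The person-time rule in SAP 4.6 uses the last dose, which favours 26.

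Anti-HBc-positive participants are followed to V802 (Week 66), 112 days after the last dose. Their uncovered span is 112 − 30 = 82 days or 112 − 44 = 68 days.

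**3. Drug remaining when the window closes.** Fraction remaining = 0.5^(t / half-life), assuming simple first-order decline from the last dose at the protocol's mean half-life.

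| Days off drug | Half-life 8 days | Half-life 13 days |
|---|---|---|
| 30 | 7.4% | 20.2% |
| 44 | 2.2% | 9.6% |
| 56 | 0.8% | 5.0% |

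These are concentrations. Neither document gives a duration of effect.

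**4. A serious infection starting 40 days after treatment discontinuation.** The SAE table covers treatment and follow-up, so it is counted there. The incidence rate takes only events within 30 days, so it is not counted there. If discontinuation means disposition at Week 52, the event falls 54 days after the last dose, still before V801.

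**5. Events and person-time in one rate.** For an event-free completer, person-time ends at Day 351 + 30 = Day 381. If discontinuation means disposition, events count to Day 365 + 30 = Day 395. For 14 days an event can enter the numerator while event-free participants add nothing to the denominator. Against 381 days of observation that is 14 / 381 = 3.7% of a completer's time. If both rules mean the last dose, the difference is zero.

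**The case against.** The strongest reply is that the SAP is wider than the protocol on TEAEs: the protocol uses the treatment period only, and the SAP adds a 30-day tail. That stands, and it removes the broadest reading. A reader might infer that no non-serious event in the washout reaches a by-arm table. In fact the first 30 days after discontinuation do, covering 30 or 44 of the 56 days since the last dose.

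A reader might also infer that only SAEs are summarised beyond 30 days. The SAP does not support this:

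- Laboratory high and low results count "at any time during the treatment period and up to 60 days after treatment discontinuation" (4.6.5).
- ALT, AST and ALP elevations cover treatment and follow-up (4.6.5.1).
- Categorical vital signs use follow-up values (4.6.6).
- Malignancies are included whatever the gap since the last dose (4.6.3.3).

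Three further readings go beyond the text. The protocol does not say that follow-up runs to V801 because drug effect carries over; it speaks of safety monitoring and washout. Nothing shows that early stoppers or Week 26 nonresponders are most affected. Early stoppers include placebo participants, and Week 26 nonresponders have all been on LY3471851, so they offer no concurrent placebo contrast. Nor does either document require AE and laboratory windows to match, so moving the TEAE window to 60 days or to V801 is a matter of choice.

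Finally, no data are lost, and SAP 4.6 says in general terms that all safety data will be summarised by treatment group. Both are true, but a general sentence does not specify a table when the section on late events names only a listing.

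**Conclusion.** The concern holds in a limited form. Non-serious AEs starting more than 30 days after treatment discontinuation get a listing and no named by-arm summary, which departs from protocol 9.4.4 and is not declared. For a completer the gap is the last 26 days before V801, or about 12, depending on an anchor date that the SAP leaves undefined. The special-interest rates share the 30-day limit and so can disagree with the SAE table. Their event and person-time rules may also differ by 14 days.

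The conclusion rests on the text and the visit calendar. It does not depend on the half-life figures, which only put the uncovered period in context. The documents give no event rates for follow-up, so the number of events affected cannot be estimated.

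**What to change.** - **SAP 4.6.2.** Keep the 30-day TEAE window. Add a summary of follow-up-emergent AEs from the end of that window to the last follow-up visit, by treatment at last dose and shown separately from TEAEs.
- **SAP 4.6 and 4.6.2.1.** State whether treatment discontinuation means the last dose or the disposition date. In the incidence rates, use that one date for both events and person-time. Note beside the serious-infection rate that the SAE table runs through follow-up.
- **SAP 1 and 4.9.** If the sponsor prefers the listing alone, declare that the protocol's summary has been dropped and give the reason.

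The cost is some wording and one more table from data already collected. The drawback is that some late events may reflect a UC flare or new UC therapy after stopping, which is why the follow-up window should be shown separately.
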